
Study Coordinator [name] Cancer Clinical Trials Office Stanford University Medical Center [REDACTED] [REDACTED] [REDACTED] [REDACTED]
	
Study Coordinator [name] Cancer Clinical Trials Office Stanford University Medical Center [REDACTED] [REDACTED] [REDACTED]

IRB number: IRB-43013

OnCore: ENT0065

IND number: [REDACTED]

Document History	
Version Date	Notes
29 September 2017	Version submitted to IRB
26 October 2017	SRC Pre-Review Comments
30 November 2017	SRC Comments + Adding Device Appendix
3 October 2018	
 Clarification of cohort structure and recruitment based on NCCN guidelines version January 2018 for use of Sentinel Node Biopsy (SNB) in head and neck cancer. (Cohort 1 – T1-2 and N0, Cohort 2 – any T and N+) Clarification that panitumumab-IRDye800 infusion will be 1 to 5 days before surgery, not 2 to 5 days before surgery Clarification of the rationale for use of panitumumab-IRDye800 Addition of additional description/clarification of SNB and neck dissection procedure for cohort 1 and 2 respectively. AEs will be graded according to CTCAE v5.0, not 4.03 Clarification of additional PKs to be collected on days 1-3 post-operation per availability up to once per day on days 1, 2, and 3 post-operation. Removed [name] as study coordinator Updated fluorescence imaging device (Appendix B) list to reflect incorporation of upgraded devices: 
 Spy-Phi for intraoperative in vivo and ex vivo imaging FIGS for intraoperative in vivo and ex vivo imaging (Stand-alone) da Vinci Firefly for intraoperative ex vivo imaging and laboratory imaging VEVO LAZR-X for intraoperative in vivo and ex vivo imaging and laboratory imaging Removal of SPY/LUNA imaging devices
26 September 2019	
 Change of Principal Investigator / Protocol Director from [name] to [name]. [name] is now listed as co-investigator. Personnel update: Included [name] and [name] as study coordinators. Other personnel changes are only made in eProtocol. Protocol modifications: 
 Removal of “Received an investigational drug within 30 days prior to first dose of panitumumab-IRDye800” as an exclusion criteria (Section 3.2 and Appendix A). Addition of photoacoustic imaging as correlative study (as discussed in IRB-35064). Update Appendix B to reflect the most recent fluorescence imaging devices (also updated in eProtocol). Administrative changes.

15 November 2019	
 Administrative changes 
 Changed [name] (now co-I) to [name] in Appendix A: Participant Eligibility Checklist Changed “Sponsor-Investigator” to “Sponsor” in Section 7 and Section 11.1
9 December 2019	
 Removed [name] as CRC, addition of [name] as CRC
1 February 2021	
 Based on published Panitumumab-IRDye800 QTc interval safety data, Day 0 and Day 15 ECGs have been removed Clarified expected Adverse Event collection window to only designated study dates Adverse Event and Serious Adverse Event reporting clarification Day 1 to 3 Post-operative (optional visit) has been removed from Study Calendar

TABLE OF CONTENTS

PROTOCOL SYNOPSIS	7
STUDY SCHEME.....	9
LIST OF ABBREVIATIONS AND DEFINITION OF TERMS.....	10
1. OBJECTIVES.....	11
1.1. PRIMARY OBJECTIVE	11
1.2. SECONDARY OBJECTIVE	11
2. BACKGROUND.....	11
2.1 STUDY DISEASE	11
2.2 STUDY AGENTS.....	15
2.3 RATIONALE.....	15
2.4 STUDY DESIGN.....	16
2.4.1. Number of subjects	16
2.4.2. Dosing	16
2.4.3. Workflow of the Clinical Trial	18
2.4.3.1. Panitumumab-IRDye800 Infusion	18
2.4.3.2. Preoperative Sentinel Node Mapping	18
2.4.3.3. Intraoperative Imaging Protocol	19
2.4.3.5. Pathological Correlates	21
3. PARTICIPANT SELECTION AND ENROLLMENT PROCEDURES.....	22
3.1 INCLUSION CRITERIA	22
3.2 EXCLUSION CRITERIA	22
3.3 INFORMED CONSENT PROCESS	23
3.4 ENROLLMENT PROCESS	23
3.5 STUDY TIMELINE.....	23
4. TREATMENT PLAN	23
4.1 TREATMENT SCHEDULE.....	23
4.2 ADMINISTRATION OF PANITUMUMAB-IRDYE800	23
4.3 ADMINISTRATION OF LYMPHOSEEK (^{99m} Tc-TILMANOCEPT).....	24

INVESTIGATIONAL PRODUCT	
A panitumumab-IRDye800 dose of 50 mg, will be systemically infused 1 to 5 days before surgery. Panitumumab-IRDye800 has been manufactured under current good manufacturing practice (cGMP) by LICOR Biosciences Inc. [name] (co-PI) currently holds the IND (119474).
 
On the day before surgery 2 mCi Lymphoseek (^{99m}Tc-tilmanocept) will be administered locally around the primary tumor for sentinel node mapping. Lymphoseek is obtained in unit doses from Cardinal Health.

TREATMENT SCHEDULE	
A panitumumab-IRDye800 dose of 50 mg, will be systemically infused 1 to 5 days before surgery. On the day before surgery, to subjects undergoing sentinel node biopsy, the standard dose of ~2 mCi Lymphoseek will be administered locally around the primary tumor after which lymphoscintigraphy and SPECT/CT imaging will be performed per standard of care to determine the number and location of foci of radiopharmaceutical uptake indicating sentinel nodes.
 
On the day of surgery, intraoperative fluorescence imaging will be performed using an intraoperative optical imaging device (a list of devices is provided in Appendix B). Per standard of care, for the subjects undergoing sentinel node biopsy, a gamma probe will be used to search for radioactive lymph nodes as well. Ex vivo fluorescence imaging and gamma counting of the excised specimens will be performed prior to and after pathological assessment. At all steps, equipment will be used that does not violate or destroy the pathological tissues.

PRIMARY OBJECTIVE(S)	The primary objective of the study is to determine if near-infrared fluorescence imaging of panitumumab-IRDye800 can identify metastatic disease in regional neck lymph nodes of subjects with head and neck squamous cell carcinoma (HNSCC).
SECONDARY OBJECTIVE(S)	Determine if panitumumab-IRDye800 can identify sentinel nodes with the same accuracy as Lymphoseek.

SAMPLE SIZE AND STUDY DURATION	
It is anticipated that 20 subjects will be enrolled into the study. Each subject will be followed for 30 days following the last dose of study medication. Based on the enrollment rate from the panitumumab-IRDye800 trial in HNSCC, it is anticipated that the study will require 2 years to be completed.

STATISTICAL CONSIDERATIONS	
To answer the primary objective we will calculate the sensitivity and specificity of the intraoperative findings on whether the lymph node is fluorescent (ie, presence of panitumumab-IRDye800) to the histopathological (gold standard) status of the lymph nodes.
 
Analysis for the secondary objective: We will determine if panitumumab-IRDye800 can identify sentinel nodes with the same accuracy as Lymphoseek. Similar to the primary analysis, we will calculate the specificity and sensitivity of Lymphoseek for metastatic lymph node identification, using histology as the gold standard, and compare these to the fluorescence imaging-based results. Since false negatives are of particular concern, we will calculate the diagnostic odds ratio to better understand the odds of obtaining a false negative using panitumumab-IRDye800 relative to the odds of obtaining a false negative using Lymphoseek-based sentinel node biopsy.

STUDY SCHEME

[figure not shown]

Figure 1. Schematic overview of the clinical trial in which we will directly compare panitumumab-IRDye800 to the reference standards sentinel node biopsy and neck dissection. Key steps of the clinical study are mentioned.

LIST OF ABBREVIATIONS AND DEFINITION OF TERMS

^{99m} Tc	Technetium-99m
AE	Adverse Event
BID	Twice Daily
BSA	Body Surface Area
CBC	Complete Blood Count
CI	Confidence Interval
CMAX	Maximum Concentration of Drug
CNS	Central Nervous System
CRF	Case Report/Record Form
CT	Computed Tomography
CTCAE	Common Terminology Criteria for Adverse Events
DLT	Dose-Limiting Toxicity
DSMC	Data Safety Monitoring Committee
ECG	Electrocardiogram
ECOG	The Eastern Cooperative Oncology Group
EGFR	Epidermal Growth Factor Receptor
eLND	Extensive Lymph Node Dissection
FDA	Food and Drug Administration
GMP	Good Manufacturing Practice
Hgb	Hemoglobin
HNSCC	Head and Neck Squamous Cell Carcinoma
HTN	Hypertension
ICG	Indocyanine green
ILD	Interstitial Lung Disease
IND	Investigational New Drug
IRB	Institutional Review Board
IV	Intravenous
LLN	Lower Limit of Normal
LN	Lymph Node
MTD	Maximum Tolerated Dose
NIR	Near-Infrared
NHS	N-hydroxysuccinimide
PAI	Photoacoustic imaging
PLT	Platelet
ROI	Region of Interest
SAE	Serious Adverse Event
SN	Sentinel Node
SNB	Sentinel Node Biopsy
SNR	Signal to Noise Ratio
SPECT	Single Photon Emission Computed Tomography
TBR	Tumor to Background Ratio
ULN	Upper Limit of Normal
UNK	Unknown
WBC	White Blood Cell
WHO	World Health Organization

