Sentinel node biopsy vs elective regional node dissection: Besides decreased morbidity, SNB offers other advantages over a neck dissection: i) Identification of aberrant draining patterns and “skip metastasis” (35–37); and ii) Improved (micro-) metastasis identification at (histo-)pathology; fewer SNs are harvested which are more meticulously evaluated by the pathologist, resulting in improved diagnostic accuracy (38,39). However, challenges remain: i) Local tracer injection is complicated in areas deep in the oral cavity; ii) Near-injection site SN identification can be challenging due to overshadowing of signal at the primary tumor signal (40,36,22); iii) Often multiple SNs are identified during surgery (22) increasing the risk of complications (41) (eg, nerve damage, lymphedema, scar tissue formation); iv) neck dissection after a positive SNB is complicated due to the presence of scar tissue; and v) A false-negative SNB occurs in 3 to 10% of subjects (ie, the SN is tumor-negative, but at follow-up metastasis in remaining regional LNs are found (42–45). Moreover, although LN mapping is superior to radiographic and clinical exam, it is still limited by the need for direct injection of the dye or radiolabeled compound. **Upstaging with LN assessment can thus only be assessed in tumor types that are accessible for local injection.** This is significant because it influences standard of care (LN surgery or complete lymphadenectomy) in these subject populations only. Identification of regional disease will inform prognostic information and/or determine the need and extent of adjuvant therapies for additional tumor types. Most importantly, however, the tracers used for SNB are not tumor-specific and thus SNB, similar to neck dissection, does not allow for intraoperative tumor-positive LN identification (21,46,47). In fact, **for both SNB and neck dissection (histo-)pathological evaluation is required to determine the presence of (micro-) metastasis and thus a method to intraoperatively identify metastatic LNs is lacking.** Thus, HNSCC subjects would benefit from an alternative technique that, allows for intraoperative lymph node staging.

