3. Hereafter, as per standard of care, the surgeon will perform SNB using the gamma probe. For this, the surgeon will evaluate the neck with the gamma probe for the presence of radioactive nodes. Upon localizing of radioactive nodes, the count rate of the node will be determined. Then, just prior to the resection of the radioactive node, *in situ* fluorescence imaging will be performed to evaluate the fluorescence-based visibility of the node. For each radioactive node, the respective *in situ* location will be documented (level Ia, Ib, IIa, IIb, III, IV or V) as well as the radioactive status (count rate) and fluorescence status (yes/no). Hereafter the node will be harvested by the surgeon. This process will be repeated until no radioactive nodes are detected anymore *in situ*.

Step 2) Wound bed imaging:

As per standard of care SNB, upon completion of SNB, the neck will be screened once more with the gamma probe as such to determine the presence of any remaining radioactivity (ie, a radioactive signal detected > 10% of the background that correlates with any substrate (node). Areas in the wound bed determined radioactive-positive will be surgically re-evaluated, and, upon checking the fluorescence-status, removed, if deemed necessary by the surgeon. If any nodes are found, gamma tracing will be performed to determine the radioactive status.

Step 3) Pathological imaging:

The fluorescence and/or radioactive status of all excised nodes will be confirmed *ex vivo* on the back table using both a closed-field imaging device and an open-field device as well as the gamma probe, respectively. Hereafter all excised nodal specimens will be sent for (histo-)pathology. After the tissue has been processed and evaluated by the pathologist, imaging findings will be compared to gold-standard histological-assessment performed by the pathologist (including a hematoxylin and eosin (H&E) staining) to determine the correlation between fluorescence, radioactivity and the presence/absence of tumor tissue in the LN(s). Also findings will be compared to preoperative lymphoscintigraphy and SPECT/CT imaging (ie, correlation between preoperative imaging findings and intraoperative imaging findings).

Neck dissection only (T1-4, cN+)

After the neck has been opened by the surgeon, it will be inspected by the surgeon for the presence of suspicious nodes. Real-time fluorescence imaging of the LNs in the neck will then be performed at 4 time points:

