12. STATISTICAL CONSIDERATIONS

12.1 Statistical Design

12.1.1. Primary Objective and Endpoint

The **primary objective** of the study is to determine if near-infrared fluorescence imaging of panitumumab-IRDye800 can identify metastatic disease in regional neck LNs of subjects with HNSCC.

The **primary endpoint** is: The number and location of panitumumab-IRDye800 positive LNs that are also tumor-positive at (histo-)pathology.

To **answer the primary objective**, we will calculate the sensitivity and specificity of the intraoperative findings on whether the LN is fluorescent (ie, presence of panitumumab-IRDye800) to the histopathological (gold standard) status of the LNs.

We will use the matched pair Durkalski's test (80), accounting for the cluster-correlation within subject, for all sensitivity and specificity comparisons (primary and secondary) using the clust.bin.pair package (81) in the R statistical software (84). Significance for both primary and secondary analyses will be assessed at the 0.05 level and to assess uncertainty, 95% confidence intervals will be provided for all estimates.

Descriptive statistics for continuous characteristics (eg, size of the tumor compartment) will include mean, standard deviation, median, interquartile range, minimum, and maximum values. Frequencies and percentages will be used to summarize categorical data. Graphical tools such as heat maps, histograms, and boxplots will be used to assess distributional properties of continuous variables.

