12.1.3. Sample Size Justification and Power Considerations

We expect to enroll 10 T1/T2 node-negative subjects and 10 subjects with T1-4 and LN metastasis. Based on the data on LN collection from our current IRB-35064 study, we expect that 50% of subjects will undergo a bilateral neck dissection, meaning we would have a total of 30 necks. Assuming an average of 20 LN harvested per neck we would have a total of 600 LNs. Based on previous findings from our IRB-35064 study, we expect approximately 30-40% of subjects (6 to 8 of 20) will have metastatic LNs with an overall prevalence of 5 to 10% of the total number of harvested LNs (30 to 60 of 600) being tumor-positive.

Since this is a Phase 2 study, power considerations are limited but even so, we have excellent power to detect differences in specificity. Although we will use Durkalski's test to compare sensitivities and specificities, we estimated power by first determining the effective sample size (ESS), adjusting for the correlation of LNs within person, and then estimated power using McNemar's test on this ESS. We assumed an intra-class correlation of 0.005, yielding an effective sample size of 524 LNs. With an effective sample size of 524, a prevalence of 7.5%, a significance level of 0.05, and a 0.25 proportion of discordant pairs, we have greater than 99% power to detect a 0.1 difference in specificities, assuming the lower specificity is 0.8. Similarly, we have greater than 78% power to detect a 0.2 difference in sensitivity with the one-sided McNemar test. This assumes the proportion of discordant pairs is 0.25 and the lower sensitivity is 0.75.

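### Cohort 1 nodes reach histology because they are radioactive, so Lymphoseek's specificity is near 0 by selection and the planned test of it against fluorescence is decided by node choice, while the synopsis, workflow and Section 12 disagree on comparator and node set

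*Combined protocol and SAP*

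**What the plan says.** **Comparison and test.** The synopsis sets Lymphoseek against fluorescence on both measures, with histology as reference: "specificity and sensitivity of Lymphoseek for metastatic lymph node identification, using histology as the gold standard, and compare these to the fluorescence imaging-based results". Section 12.1.1 assigns Durkalski's clustered matched-pair test "for all sensitivity and specificity comparisons (primary and secondary" and adds: "Significance for both primary and secondary analyses will be assessed at the 0.05 level".

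**Who has paired data.** In Table 1 (Section 2.4.2) only Cohort 1 receives Lymphoseek. Section 3.1 makes the two cohorts mutually exclusive: sentinel node biopsy (SNB) only, or neck dissection only.

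**How Cohort 1 nodes reach histology (Section 2.4.3.3).** "Hereafter, as per standard of care, the surgeon will perform SNB using the gamma probe". Radioactive nodes are harvested, and "This process will be repeated until no radioactive nodes are detected anymore". Wound-bed re-evaluation is also triggered by radioactivity. Fluorescent nodes seen on opening are recorded on a photograph, with no step to excise them on that ground. Only excised nodes go to pathology.

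**Nature of the tracer.** Section 2.1 states that "the tracers used for SNB are not tumor-specific".

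**Conflicting text.** Section 12.1.2 compares Lymphoseek with neck dissection, not with fluorescence. Section 12.1.3 starts from "We expect to enroll 10 T1/T2 node-negative subjects and 10 subjects with T1-4 and LN metastasis", then counts 30 necks at 20 nodes each, 600 in all, as if both cohorts had dissections. On that basis it says "we have excellent power to detect differences in specificity".

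**The concern.** Specificity is computed on tumor-free nodes. If a node is in the data because it was radioactive, every tumor-free node is a Lymphoseek false positive, however well the tracer performs. Each tumor-free node that does not fluoresce then scores for panitumumab-IRDye800, and almost none can score the other way, since that needs an excised node that is fluorescent but not radioactive. The test asks only whether some tumor-free sentinel nodes stay dark. It says nothing about whether fluorescence follows tumor.

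The same selection pushes Lymphoseek's sensitivity towards 1. The planned odds of a false negative with one tracer relative to the other therefore cannot be estimated from these nodes either.

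At stake is a secondary result, formally significant at 0.05, that could be reported as a specificity advantage when it reflects the harvest rule.

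**Working it through.** **1. The plan's own figures (Section 12.1.3).**
- Effective sample size: 600 / (1 + 29 × 0.005) = 600 / 1.145 = 524, taking 600/20 = 30 nodes per subject. This reproduces.
- Specificity: n = 524 × 0.925 = 484.7, difference 0.1, discordance 0.25, two-sided 0.05. z = (0.1√484.7 − 1.96√0.25) / √(0.25 − 0.01) = 2.49, power 99.4%. This reproduces the claim of more than 99%.
- Sensitivity: n = 524 × 0.075 = 39.3, difference 0.2, one-sided. Power is 76.8% exact and 82.7% by the same normal approximation, consistent with the stated figure of more than 78%.

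The arithmetic is sound. The question is whether its node set exists for the tracer comparison.

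**2. What the Cohort 1 workflow supplies.** Ten subjects. Radioactive nodes per subject are not given; I assume a mean of 2, 3 or 4, so about 20 to 40 nodes rather than 600. Let q be the share of tumor-free sentinel nodes that fluoresce. Lymphoseek specificity is 0, dye specificity is 1 − q, and the discordant share is 1 − q: 0.927 at q = 7.3%, 0.8 at q = 20%. The power section assumes a lower specificity of 0.8 and discordance of 0.25.

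**3. The test.** The documents do not print the statistic; I use its standard form over tumor-free nodes:

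T = [Σ(b_k − c_k)/n_k]² / Σ[(b_k − c_k)/n_k]², significant if T > 3.84.

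Here b_k counts radioactive dark nodes and c_k non-radioactive fluorescent nodes in subject k. Sidedness is not stated for specificity; two-sided is assumed. With c_k = 0 and the same dark share p in all 10 subjects, T = (10p)² / (10p²) = 10, p-value 0.0016, however small p is.

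**4. Simulation under no tumor information.** The dye lights any node with probability q whatever its tumor status. There are 10 subjects, 1 + Poisson(mean − 1) radioactive nodes each, and 4,000 trials per setting in the main runs. The table gives the percentage of trials declaring fluorescence more specific. Ranges cover separate runs that differ in how tumor-positive nodes were placed (for example, 20% of subjects with one positive node, or 7.5% of nodes positive) and in simulation error.

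| q | mean 2 | mean 3 | mean 4 |
|---|---|---|---|
| 7.3% | 100 | 100 | 100 |
| 20% | about 100 | 100 | 100 |
| 50% | 90–93 | 98–99 | >99 |
| 70% | 48–52 | 77–79 | 92–94 |
| 80% | 19–23 | 44–46 | 67 |
| 90% | 3 | 8–9 | 18 |

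The 7.3% is 1 − 0.927, from the cetuximab-IRDye800 specificity quoted in Section 2.1. The 20% is 1 − 0.8, from the power section. A dye lighting 7.3% of nodes at random has sensitivity 0.073 and specificity 0.927, so sensitivity + specificity − 1 = 0, yet it wins this test.

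**5. Sensitivity to assumptions.**
- If 10% of excised nodes are non-radioactive (mean 3): above 99% at q = 7.3%, 99% at 20%, 77% at 50%, 31% at 70%.
- If non-radioactive nodes are added at 0.2 per radioactive node (means 2/3/4): Lymphoseek specificity is about 0.16, with 65/80/89% at q = 50% and 14/20/27% at 70%.
- If fluorescence clusters within subject (assumed correlation 0.3): 88/96/98% at q = 50%.

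**6. The other node set.** Suppose Cohort 1 supplied 15 necks × 20 = 300 nodes, as Section 12.1.3 implies. With 3 radioactive nodes per subject, Lymphoseek specificity is about 1 − 30/300 = 0.90 (0.93 with 2, 0.87 with 4). The same dye at q = 20% is then declared more specific in 0% of runs. It is declared less specific in 61% (five subjects with 20 nodes, five with 40) to about 90% (30 nodes each). At q = 7.3% it is declared more specific in roughly 12 to 18%. The dye is unchanged; only the nodes differ.

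**The case against.** **The test is assembled from two places.** The synopsis names no test, and Section 12.1.2, which specifies the secondary analysis, sends Lymphoseek to a comparison with neck dissection. This stands as a conflict to be resolved. It does not remove the comparison: the synopsis states it, Section 12.1.1 covers all such comparisons, and the SNB workflow contains no neck dissection to compare with.

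**Cohort 1 may have been meant to have dissections.** Section 12.1.3 counts nodes that way, and Section 4.5 speaks of imaging before and after lymphadenectomy. The detailed workflow and the SNB-only label are the stronger text, but the contradiction is real and step 6 shows that it reverses the result.

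**A reader might infer that Section 12.1.3 claims excellent power for this comparison.** The text does not support that. It never says which comparison is powered, and its inputs cannot describe a Lymphoseek specificity near 0.

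**A reader might infer that the trial would call a useless dye a success.** The documents contain no superiority rule or success criterion on specificity alone. The stated aim is equal accuracy, sensitivity is compared alongside, false negatives are singled out, and the primary analysis estimates fluorescence sensitivity against histology. A dye that missed most metastases should show up there.

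**A reader might infer that the false advantage is guaranteed.** It is not. Section 2.4.3.5 expects non-specific uptake by a mechanism like sentinel node mapping, so q in these nodes may be high. The 7.3% anchor comes from a different agent and is not specific to sentinel nodes.

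**Conclusion.** The concern holds for the SNB workflow as written. Lymphoseek's specificity and false-negative rate are not estimable from nodes selected for radioactivity, and the 0.05 test of its specificity against fluorescence reflects that selection.

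The chance that an uninformative dye is declared more specific falls below one half at q of about 70 to 80% or more for a mean of 2 to 3 nodes, or about 60 to 70% for a mean of 3 if 10% of nodes are non-radioactive. Nodes per subject, q, the share of non-radioactive nodes, two-sidedness and the form of the statistic are assumptions.

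The synopsis, Section 2.4.3.3, Section 12.1.2 and Section 12.1.3 cannot all be right about the comparator and the Cohort 1 nodes. The harm is limited to a secondary analysis in a 20-subject exploratory study, but the plan should be corrected.

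**What to change.** 1. Reconcile the synopsis, Section 2.4.3.3, Section 12.1.2 and Section 12.1.3: name one comparator for Lymphoseek and state which Cohort 1 nodes have histology and enter the analysis. Nothing here bears on which operation is appropriate.
2. If the SNB workflow stands, delete the test of Lymphoseek specificity against fluorescence specificity. State that Lymphoseek's specificity and false-negative rate, and hence the false-negative odds comparison, are not estimable from radioactivity-selected nodes.
3. In its place, report among radioactive Cohort 1 nodes the sensitivity and specificity of fluorescence, and sensitivity + specificity − 1, with subject-clustered 95% intervals, as exploratory estimates. The last quantity is 0 for a dye that lights nodes at random. Section 12.1.1 already plans intervals for the first two; the restriction to radioactive nodes and the combined measure are new.
4. State in Section 12.1.3 that the power figures, which rest on 600 nodes and a lower specificity of 0.8, do not apply to the Cohort 1 tracer comparison.

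The cost is wording only, with no new data or subjects. A formal secondary test is lost, and with few positive nodes expected in Cohort 1 the replacement estimate will be imprecise.
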